9.3.2. Access to Information for Monitoring

In accordance with regulations and guidelines, the study monitor must have direct access to the investigator's source documentation in order to verify the accuracy of the data recorded in the eCRF.

The monitor is responsible for routine review of the eCRF at regular intervals throughout the study to verify adherence to the protocol and the completeness, consistency, and accuracy of the data being entered on them. The monitor should have access to any subject records needed to verify the entries on the eCRF. The investigator agrees to cooperate with the monitor to ensure that any problems detected through any type of monitoring (central, on site) are resolved.

9.3.3. Access to Information for Auditing or Inspections

Representatives of regulatory authorities or of Gilead may conduct inspections or audits of the clinical study. If the investigator is notified of an inspection by a regulatory authority the investigator agrees to notify the Gilead medical monitor immediately. The investigator agrees to provide to representatives of a regulatory agency or Gilead access to records, facilities, and personnel for the effective conduct of any inspection or audit.

9.3.4. Study Discontinuation

Both the sponsor and the investigator reserve the right to terminate the study at any time. Should this be necessary, both parties will arrange discontinuation procedures and notify the appropriate regulatory authority(ies), IRBs, and IECs. In terminating the study, Gilead and the investigator will assure that adequate consideration is given to the protection of the subjects' interests.

11. APPENDICES

- Appendix 1. Investigator Signature Page
- Appendix 2. Study Procedures Table
- Appendix 3. ECOG Performance Status
- Appendix 4. Pregnancy Precautions, Definition for Female of Childbearing Potential, and Contraceptive Requirements
- Appendix 5. Revised RECIST Guideline (version 1.1)

Appendix 2. Study Procedures Table

Period	Screening	Randomization ^a	Treatment												EOT ^m	Disease Progression	EOS ⁿ	30 day Safety Follow-up ^o	5-month Safety Follow-Up ^p	Long Term Follow-Up
			3	4	5	6	7	8	9	10	11	12	13	14 to 50						
Visit	1	2	3	4	5	6	7	8	9	10	11	12	13	14 to 50						
Week	-4	Day 1	2	4	6	8	10	12	14	16	18	20	22	24 to 96						
Window (day)	-28		±3	±3	±3	±3	±3	±3	±3	±3	±3	±3	±3	±3			±7	±7	±7	
Informed Consent	X																			
Medical and Medication History	X																			
Physical Examination ^b	X	X		X		X		X		X		X		X ^s	X		X	X		
Vital Signs & Weight	X	X	X	X	X	X	X	X	X	X	X	X	X	X	X		X	X		
ECOG Performance Status ^c	X	X ^c		X		X		X		X		X		X ^s	X		X	X		
12-lead ECG	X	X		X		X		X		X		X		X ^s	X		X			
Adverse events/ Concomitant Medications ^d	X	X	X	X	X	X	X	X	X	X	X	X	X	X	X	X	X	X	X	
IWRS Registration	X	X	X	X	X	X	X	X	X	X	X	X	X	X	X		X			
Study Drug/ Nivolumab Administration ^e		X	X	X	X	X	X	X	X	X	X	X	X	X						
Hematology	X	X	X	X	X	X	X	X	X	X	X	X	X	X	X		X	X	X	

Period	Screening	Randomization ^a	Treatment												EOT ^m	Disease Progression	EOS ⁿ	30 day Safety Follow-up ^o	5-month Safety Follow-Up ^p	Long Term Follow-Up
			3	4	5	6	7	8	9	10	11	12	13	14 to 50						
Visit	1	2	3	4	5	6	7	8	9	10	11	12	13	14 to 50						
Week	-4	Day 1	2	4	6	8	10	12	14	16	18	20	22	24 to 96						
Window (day)	-28		±3	±3	±3	±3	±3	±3	±3	±3	±3	±3	±3	±3			±7	±7	±7	
Chemistry	X	X	X	X	X	X	X	X	X	X	X	X	X	X	X		X	X	X	
Thyroid Function Tests (TSH, T3, free T4)	X					X				X				X ^t	X		X	X	X	
Coagulation	X														X		X			
Urinalysis	X	X		X		X		X		X		X		X ^s	X		X	X	X	
Pregnancy Test ^f	X	X		X		X		X		X		X		X ^s	X		X	X	X	
Andecaliximab PK ^g		X		X		X				X				X ^t	X		X			
Anti-Andecaliximab Antibody ^h		X		X		X				X				X ^t	X		X			
Blood Biomarkers ⁱ	X	X	X	X		X				X				X ^t		X ⁱ	X ⁱ			
Oral Sampling		X																		
CCI																				
CT or MRI & Treatment Response Assessment ^k	X					X				X				X ^t		X ^q	X			

Period	Screening	Randomization ^a	Treatment												EOT ^m	Disease Progression	EOS ⁿ	30 day Safety Follow-up ^o	5-month Safety Follow-Up ^p	Long Term Follow-Up
			3	4	5	6	7	8	9	10	11	12	13	14 to 50						
Visit	1	2	3	4	5	6	7	8	9	10	11	12	13	14 to 50						
Week	-4	Day 1	2	4	6	8	10	12	14	16	18	20	22	24 to 96						
Window (day)	-28		±3	±3	±3	±3	±3	±3	±3	±3	±3	±3	±3	±3			±7	±7	±7	
Tumor Biopsy ^l	X ^l			X ^l (Wk 5 through Wk 9)												X ^l				
Overall Survival and Other Antitumor Therapy																				X ^u

- a Day 1 visit must occur within 3 days following randomization.
- b Complete physical examination (PE) to be performed at Screening, EOT and EOS. A modified PE capturing changes from prior exams will be performed at subsequent visits. Height is required at Screening only.
- c ECOG performance status on Day 1 may be waived if has been conducted during screening within 4 days of Day 1.
- d Adverse events will be assessed and concomitant medications will be recorded at each clinic visit from Screening up to and including the 30-day Safety Follow-up visit or EOS visit whichever is later.
- e For Arm A: Study drug andecaliximab (800 mg) will be administered via IV infusion every 2 weeks over 30 (± 5) min. Nivolumab (3 mg/kg) will be administered via IV infusion following the completion of andecaliximab every 2 weeks over 60 (± 5) min. For Arm B: Nivolumab alone (3 mg/kg) will be administered via IV infusion every 2 weeks over 60 (± 5) min.
- f If applicable (females of child bearing potential). Serum pregnancy testing will be conducted at Screening. Urine pregnancy testing will be conducted pre-dose on Day 1 and then every 4 weeks, at EOT, and EOS, 30-day, and 5-month Safety Follow-up.
- g For Arm A only, plasma samples will be collected for andecaliximab PK at 30(± 15) min after the end of infusion on Day 1. For Weeks 4, 8, 16, and 24 and every 3 months thereafter, PK will be collected prior to dosing and 30(± 15) min after the end of infusion. It will also be collected at EOT and EOS.
- h For Arm A only, serum samples for anti-andecaliximab antibody will be collected prior to dosing on Day 1, Week 4, Week 8, Week 16, Week 24, and every 3 months thereafter, EOT and EOS.
- i Blood biomarkers will be collected at screening and prior to dosing on Day 1; Week 2; Week 4; Week 8; Week 16; Week 24 and every 3 months thereafter and at progression or EOS.
- j [REDACTED]
- k Tumor evaluation by CT or MRI will be performed during screening and approximately every 8 weeks regardless of visit week or dose interruption. Scan at EOS visit is not necessary if restaging scan is performed within the prior 8 weeks. Treatment response assessment will be per RECIST v1.1.
 For subjects who stop study treatment in the absence of disease progression (eg. experienced unexpected toxicity) and remain on study for follow up for progression-free survival, tumor evaluation by CT or MRI should continue approximately every 8 weeks until disease progression or initiation of non-study specific anti-neoplastic therapy in the absence of progression, whichever occurs earlier.

- l A pretreatment biopsy is requested if archival tumor sample provided to meet Inclusion Criterion #6 is from before the last line of therapy. An on-treatment biopsy is required between Week 5 and Week 9. A biopsy at disease progression is requested, if medically feasible. The sample should be collected by the last clinic visit on study ie EOS or 30 Day Safety Follow up visit. All biopsies are requested to be from gastric lesions if possible (non-gastric metastatic lesions ok if no gastric lesions possible). See laboratory manual for biopsy specifications and procedures.
- m End of treatment (EOT) assessments will be completed only by subjects who discontinue all treatment for reasons other than progressive disease, initiation of new anti-neoplastic treatment, or full withdrawal of consent. These assessments should be completed as soon as possible after the decision is made. Every attempt should be made to keep the subject in the study and continue to perform tumor evaluation by CT or MRI approximately every 8 weeks until disease progression.
- n End of study (EOS) assessments will be completed when a subject meets at least 1 of the criteria for study discontinuation (Section 3.7).
- o The 30-day safety follow up visit will be performed following the last dose of andecaliximab.
- p The 5-month safety follow up visit will be performed following the last dose of nivolumab.
- q If imaging shows progressive disease (PD), it is at the discretion of the investigator to keep the subject on study treatment or to stop study treatment until imaging is repeated ≥ 4 weeks later in order to confirm PD (see section 6.2.9).
- r Starting at Week 24, perform every 12 weeks until EOT/EOS.
- s Starting at Week 24, perform every 4 weeks until EOT/EOS.
- t Starting at Week 24, perform every 8 weeks until EOT/EOS.
- u Perform every 3 months until 5 years.

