5.4. Prior and Concomitant Medications

At Screening, all medication taken up to 30 days prior to the screening visit will be recorded on the eCRF. At each study visit, the site will capture any and all medications taken by the subject since the last visit or during the visit (as applicable). Concomitant medications include prescription and non-prescription medications, pre-infusion medications (eg, anti-emetics), and vitamins and minerals.

In addition, supportive therapies given during the course of the study (eg, blood transfusion, growth factor) will be collected and recorded on the eCRF.

During the course of the clinical trial, study subjects are anticipated to continue the use of prescribed medications identified during the screening procedures, consistent with study inclusion and exclusion criteria.

Non-study anticancer chemotherapy or immunotherapy (approved or investigational) is not permitted during the trial. If administered, the subject may be removed from the trial.

Inhaled steroids and short courses of oral steroids for anti-emesis or as an appetite stimulant are allowed; however, chronic daily treatment with oral corticosteroids (dose of > 10 mg/day prednisone equivalent) are not.

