5.4.1. Acceptable Concomitant Medications

All treatments that the investigator considers necessary for a subject's welfare may be administered at the discretion of the investigator in keeping with the community standards of medical care. All concomitant medication will be recorded on the case report form (CRF) including all prescription, over-the-counter (OTC), herbal supplements, and IV medications and fluids. If changes occur during the trial period, documentation of drug dosage, frequency, route, and date may also be included on the CRF.

All concomitant medications received within 30 days before the first dose of trial treatment and 30 days after the last dose of trial treatment should be recorded.

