6.2.11. Adverse Events

From the time of obtaining informed consent through the first administration of study drug, record all SAEs as well as any AEs related to protocol-mandated procedures on the AE eCRF. All other untoward medical occurrences observed during the screening period, including exacerbation or changes in medical history are to be captured on the medical history eCRF.

From the time of the first administration of study drug through 30 days post the last administration of andecaliximab and 5 months post-treatment of nivolumab, record any SAEs, and AEs including exacerbation or changes in medical history, on the AE eCRF.

See Section 7 Adverse Events and Toxicity Management for additional details.

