7.3.1. Adverse Events

Following initiation of study medication, collect all AEs, regardless of cause or relationship, until 30 days after last administration of study drug andecaliximab and 5 months post-treatment of nivolumab, must be reported to the eCRF database as instructed.

All AEs should be followed up until resolution or until the adverse event is stable, if possible. Gilead Sciences may request that certain AEs be followed beyond the protocol defined follow-up period.

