7.4.2. Concomitant Medications

Concomitant medications are defined as medications taken while a subject took study drug. Use of concomitant medications will be summarized by Anatomical Therapeutic Chemical (ATC) drug class Level 2 and preferred name using the number and percentage of subjects for each treatment group. A subject reporting the same medication more than once will be counted only once when calculating the number and percentage of subjects who received that medication. The summary will be ordered alphabetically by ATC medical class and then by preferred term in descending overall frequency within each ATC medical class. For drugs with the same frequency, sorting will be done alphabetically.

For the purposes of analysis, any medications with a start date prior to or on the first dosing date of study drug and continued to be taken after the first dosing date, or started after the first dosing date but prior to or on the last dosing date of study drug will be considered concomitant medications. Medications started and stopped on the same day as the first dosing date or the last dosing date of study drug will also be considered concomitant. Medications with a stop date prior to the date of first dosing date of study drug or a start date after the last dosing date of study drug will be excluded from the concomitant medication summary. If a partial stop date is entered, any medication with the month and year (if day is missing) or year (if day and month are missing) prior to the date of first study drug administration will be excluded from the concomitant medication summary. If a partial start date is entered, any medication with the month and year (if day is missing) or year (if day and month are missing) after the study drug stop date will be excluded from the concomitant medication summary. Medications with completely missing start and stop dates will be included in the concomitant medication summary, unless otherwise specified. Summaries will be based on the Safety Analysis Set. No formal statistical testing is planned.

All prior and concomitant medications (other than per-protocol study drugs) will be provided in a by-subject listing sorted by subject ID number and administration date in chronological order.

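### Schedule footnote d stops adverse event recording at the 30-day or EOS visit, against the 5-month window after nivolumab in its own row, the protocol text and the SAP

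*Protocol*

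**What the plan says.** **The footnote.** In Protocol Appendix 2 the row "Adverse events/ Concomitant Medications ^d" carries footnote d, which has both items recorded at clinic visits "from Screening up to and including the 30-day Safety Follow-up visit or EOS visit whichever is later". SAP Appendix 2 repeats the footnote word for word. It does not mention the 5-month visit.

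**The grid.** The same row is marked in every column from Screening through the 5-month Safety Follow-up. Only Long Term Follow-Up is blank.

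**The AE text.** Protocol 7.3.1 has all AEs collected "until 30 days after last administration of study drug andecaliximab and 5 months post-treatment of nivolumab". Protocol 6.2.11 says the same for the eCRF: "through 30 days post the last administration of andecaliximab and 5 months post-treatment of nivolumab, record any SAEs, and AEs".

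**The analysis windows.** Protocol 8.2.1.2 and 8.6 include safety data up to the later of 30 days after andecaliximab and 5 months after nivolumab. SAP 7.1.5.1 counts treatment-emergent events over the same periods.

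**The visit anchor.** Protocol Appendix 2 states: "The 30-day safety follow up visit will be performed following the last dose of andecaliximab". Protocol 6.7 agrees. Protocol 6.8 times the 5-month visit from the last nivolumab dose.

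**Medications.** Protocol 5.4.1 limits the record to medications from 30 days before the first dose and says those received up to "30 days after the last dose of trial treatment should be recorded". Protocol 5.4 sets no such end: "At each study visit, the site will capture any and all medications taken by the subject since the last visit".

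**The concern.** Protocol Section 6 sends sites to Appendix 2 for the procedures, so a stopping rule in a footnote there can be applied as written. A site that does so stops asking about AEs at the 30-day visit or EOS, while the SAP goes on to count events to 5 months after nivolumab. Subjects with no recorded late event would then include some who were never asked.

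This bears on a stated aim, because comparing safety and tolerability between the arms is a secondary objective. It also reaches the report: SAP Section 1 bases the synoptic clinical study report on this SAP for everything except efficacy. Shortened collection that was equal in both arms would under-count late events. If its length differed by arm, it could also distort the comparison.

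**Working it through.** No figure in the plan needs reproducing. The check is a comparison of texts and then the length of the gap.

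**1. End of AE recording, source by source**

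| Source | End of AE recording or counting |
|---|---|
| Footnote d, both documents | later of 30-day visit and EOS |
| Grid row carrying footnote d | marked at the 5-month visit |
| Protocol 6.2.11 and 7.3.1 | 30 days after andecaliximab and 5 months after nivolumab |
| Protocol 8.2.1.2 and 8.6 | later of those two |
| SAP 7.1.5.1 | 30 days after andecaliximab or 5 months after nivolumab |
| Protocol 7.3.2 (serious events) | 5 months after nivolumab, any causality |

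The grid was checked for column shift. The row has 20 cells for 20 columns: 19 marks and one blank, the last. Hematology, also marked at 5 months, and vital signs, not marked there, align in the same way. The 5-month mark is therefore real.

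**2. Who is exposed**

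Progression is a reason to end study participation (Protocol 3.7), and meeting such a reason triggers the EOS assessments (6.6). A subject who stops treatment at progression would usually have both EOS and the 30-day visit well before month 5. A subject who stops without progression stays on study with scans every 8 weeks (3.6, 6.3), so EOS may fall much later.

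**3. Length of the gap**

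Inputs: 30.4375 days per month (SAP 6.2.1); a 30-day visit with a window of ±7 days (Protocol 6.7).

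- Required window: 5 × 30.4375 = 152.19 days.
- Both drugs stopped on the same day, 30-day visit on day 30, EOS no later: 152.19 − 30 = 122.19 days uncovered, and 122.19 / 152.19 = 80%.
- Visit at day 37: 152.19 − 37 = 115.19 days (76%).
- Visit at day 23: 152.19 − 23 = 129.19 days (85%).
- EOS one scan interval (56 days) after the last nivolumab dose, as an illustration: 152.19 − 56 = 96.19 days (63%).
- EOS after day 152: no gap.

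**4. By arm**

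Let *e* be the number of days from the last nivolumab dose to EOS. Arm A, with both drugs stopped together, records to the later of about day 30 and *e*. Arm B has no andecaliximab dose from which to time a 30-day visit, so read literally it records only to *e*, leaving a gap of 152.19 − *e*. When *e* is below 30, Arm B is followed for a shorter time than Arm A. When *e* is above 30, the two are equal.

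**5. Medications**

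Protocol 6.2.11 and 7.3.1 concern AEs, so they do not conflict with 5.4.1. The 30-day limit in 5.4.1 conflicts with the 5-month mark in a row that covers medications, and with the capture at every study visit in 5.4.

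**The case against.** **The footnote is one line against many.** No text ranks it above the body of the protocol. Section 6 says the procedures are tabulated in Appendix 2 and also described in the text. A site working from the grid, 6.2.11 or 7.3.1 collects to 5 months. This stands. That the tables *will* mix two collection windows is something a reader might infer, but the documents show only that they could.

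**Serious events are protected.** Protocol 7.3.2 requires serious events and deaths within 5 months after nivolumab to be reported regardless of cause. This stands, and it removes the reading that late events in general would be lost.

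**The 80% is not typical of every subject.** Those who stop for toxicity remain on study, and their EOS may extend recording past 30 days or past month 5. This stands, so the figure must be given with its conditions.

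**Protocol 8.6.2 defines treatment-emergent AEs with a 30-day limit.** That is a separate inconsistency. It does not rescue the footnote, because 7.3.1 still requires collection and 8.2.1.2, 8.6 and SAP 7.1.5.1 still use 5 months.

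**A stronger medication claim does not hold.** A reader might infer that treatment for late events goes unrecorded, or that SAP 7.4.2 wrongly discards it, since a medication with "a start date after the last dosing date of study drug will be excluded from the concomitant medication summary". But 7.3.2.1 requires medications treating a serious event to be recorded. SAP 7.4.2 deliberately defines concomitant use as use while on study drug, and it lists all recorded medications. The steroid-taper text in Protocol 3.5.1 concerns dosing interruptions before treatment restarts. A course begun in such an interruption starts before the last dose if dosing resumes, so it is summarized. An extra table of post-dose immunosuppressants would be a preference, not a correction. No body text sets a 5-month medication window against which a percentage lost could be stated.

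**Conclusion.** The contradiction is established on the text. Footnote d, in both documents, disagrees with its own grid row, with the AE collection rules and with the windows over which AEs will be analyzed.

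The exposed data are mainly non-serious AEs after the 30-day or EOS visit. About 122 of 152 days (115 to 129 with the visit window) would be missed for a subject only if the site follows the footnote, both drugs stop on the same day, the 30-day visit takes place and EOS is no later. The documents do not show how many sites or subjects would meet those conditions, so no trial-level loss can be stated.

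The possible difference between arms rests on reading the andecaliximab anchor literally. It affects subjects whose EOS comes before about day 30 after nivolumab, and it matters because the arms are to be compared on safety. The medication issue is smaller: an unreconciled end date among 5.4.1, 5.4 and the grid. The point should be corrected, but it does not show that the safety comparison is invalid.

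**What to change.** - In Protocol Appendix 2 and SAP Appendix 2, change footnote d so that recording runs up to and including the 5-month Safety Follow-up visit, or EOS if later. This matches the grid, 6.2.11 and 7.3.1, and gives both arms an end point timed from nivolumab.
- Reconcile the 30-day limit in Protocol 5.4.1 with the 5-month mark in the grid and with 5.4, so that one end date for medication recording is stated.

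The 5-month visit already exists (Protocol 6.8) and the row is already marked there, so no visit or procedure is added. The cost is a little more data entry and a protocol modification, which needs documented ethics approval before it takes effect (Protocol 9.2.1). The SAP is for a follow-up analysis after the primary one, so the change may come too late for some subjects and cannot recover events never asked about.

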Appendix 3. ECOG Performance Status

Grade	
0	Fully active, able to carry on all pre-disease performance without restriction
1	Restricted in physically strenuous activity but ambulatory and able to carry out work of a light or sedentary nature, eg, light house work, office work
2	Ambulatory and capable of all self-care but unable to carry out any work activities. Up and about more than 50% of waking hours
3	Capable of only limited self-care, confined to bed or chair more than 50% of waking hours
4	Completely disabled. Cannot carry on any self-care. Totally confined to bed or chair
5	Dead

Reference for ECOG {[Oken 1982](#)}

Appendix 4. Pregnancy Precautions, Definition for Female of Childbearing Potential, and Contraceptive Requirements

1) Pregnancy and Contraception Requirements for Males and Females of Childbearing Potential

The risks of treatment with andecaliximab during pregnancy have not been evaluated in humans. The potential for genotoxicity is not expected given that andecaliximab is a monoclonal antibody. In both the rat and rabbit definitive embryo-fetal developmental toxicity studies, there were no andecaliximab-related effects on embryo-fetal survival and growth and no fetal anomalies. In a fertility study in male and female rats, no test article-related effects on reproductive performance and intrauterine survival were observed at any dosage level. A clinically relevant interaction between andecaliximab and contraceptive steroids is not expected because of their distinct metabolic pathways and therefore, hormonal contraception may be used as part of the birth control methods.

Please refer to the latest version of the investigator's brochure for additional information.

Please refer to the regional prescribing information for information on the potential risks of treatment with nivolumab.

2) Definition of Female of Childbearing Potential

For the purposes of this study, a female subject of childbearing potential is a woman who has not had a hysterectomy, bilateral oophorectomy, or medically documented ovarian failure. This definition includes pubertal females regardless of whether or not she has had a menses (premenarchal, Tanner Stage 3) and perimenopausal women who have had a spontaneous menses in the last 12 months. A woman who has had a tubal sterilization is considered to be of childbearing potential.

- Women \leq 54 years of age with amenorrhea of any duration will be considered to be of childbearing potential unless they have had a hysterectomy, bilateral oophorectomy, or medically documented ovarian failure.
- Women $>$ 54 years of age with cessation (for \geq 12 months) of previously occurring menses due to ovarian failure will not be considered to be of childbearing potential.

3) Contraceptive Requirements for Females

Female subjects of childbearing potential must agree to use protocol specified highly effective method(s) of contraception from the screening/randomization visit throughout the study period, 90 days following the last dose of study drug andecaliximab and 5 months after the last dose of nivolumab unless the subject chooses continuous heterosexual abstinence as a lifestyle choice. The investigator should counsel subjects on the protocol specified method(s) for avoiding pregnancy during the study. See the listed below for the protocol specified contraceptive methods.

Female study subjects who are not heterosexually active must have periodic confirmation of continued abstinence from heterosexual intercourse and regular pregnancy testing while taking study drug. The investigator should counsel subjects on the protocol specified method(s) for avoiding pregnancy in case the subject chooses to engage in heterosexual intercourse.

Female subjects of childbearing potential must have a negative serum pregnancy test at screening and a negative urine pregnancy test every 4 weeks starting on Day 1, prior to receiving the dose of study drug. Lactating females must discontinue nursing before study drug administration.

Protocol specified contraceptive methods:

- Complete abstinence from intercourse. Periodic abstinence (eg, calendar, ovulation, symptothermal, post-ovulation methods) is not permitted.

Or

- Consistent and correct use of 1 of the following methods of birth control listed below, in addition to a male partner who correctly uses a condom from the date of Screening until 90 days after last dose of study drug andecaliximab and 5 months after the last dose of nivolumab:

- intrauterine device (IUD) with a failure rate of < 1% per year
- female barrier method: cervical cap or diaphragm with spermicidal agent
- tubal sterilization
- vasectomy in male partner
- implants of levonorgestrel
- injectable progesterone
- oral contraceptives (either combined or progesterone only)
- contraceptive vaginal ring
- transdermal contraceptive patch

Female subjects must agree to refrain from egg donation or egg harvesting for the purpose of fertilization during the course of the study for at least 90 days after the last dose of andecaliximab and 5 months after the last dose of nivolumab.

4) Contraceptive Requirements for Males

Male subjects must agree to use condoms and avoid sperm donation from the screening/randomization visit throughout the study period, and for at least 90 days after administration of the last dose of study drug andecaliximab or nivolumab.

5) Procedures to be Followed in the Event of Pregnancy

Subjects should be instructed to notify the investigator if they (or their partner) become pregnant at any time during the study, or if they become pregnant within 90 days following the last dose of andecaliximab and within 5 months after the last dose of nivolumab. Subjects who become pregnant or who suspect that they are pregnant during the study must report the information to the investigator and discontinue study drug immediately. The investigator should report all pregnancies to the CRO Safety Department using the pregnancy report form within 24 hours of becoming aware of the pregnancy. The investigator should counsel the subject regarding the possible effects of prior study drug exposure on the fetus and the need to inform the study site of the outcome of the pregnancy. Subjects whose partner has become pregnant or suspects she is pregnant during the study must report the information to the investigator. Instructions for reporting partner pregnancy, pregnancy and pregnancy outcome are outlined in Section [7.7.2.1](#).

